16.3 Hypothesis Tests

16.3.1 Treatment Comparisons

In order to preserve the Type 1 error associated with multiple endpoints (per FDA guidance), all efficacy endpoints will be evaluated in this pre-defined order: (1) MADRS through Week 6. Each will be hypothesis testing driven.

16.3.2 Primary Hypothesis

MADRS

The primary study hypothesis is that treatment with NRX-101 is superior to lurasidone in improving symptoms of depression as measured by the MADRS over 6 weeks of treatment. The primary study hypothesis is that treatment with NRX-101 is superior to lurasidone in improving

symptoms of depression as measured by the MADRS over 6 weeks of treatment. The null hypothesis for the primary endpoint is the mean change from baseline of MADRS-10 for NRX-101 is the same as lurasidone. Baseline is defined as MADRS-10 score at study entry.

The null hypothesis is no difference in the mean change in the MADRS-10 score from baseline to Day 42/exit between both treatment groups, while the alternative hypothesis is that there is a larger mean improvement in the NRX-101 group than the lurasidone group. The study is to have 80% power to detect a 0.66 effect size post-baseline for a two-sided test with 5% Type 1 error using mixed model repeated measures (MMRM).

16.3.3 Key Secondary Hypotheses

The key secondary hypothesis are that:

- treatment with NRX-101 is superior to lurasidone in improving symptoms of suicidality as measured by the CGI-SS over 6 weeks of treatment. The null hypothesis for the primary endpoint is the mean change from baseline of CGI-SS for NRX-101 is greater than or equal to the mean change from baseline of CGI-SS for lurasidone while the alternative hypothesis is that the mean change from baseline of CGI-SS is less than the mean change from baseline of CGI-SS for lurasidone (improvement). Baseline is defined as CGI-SS score at this study entry.
- that NRX-101 is superior to lurasidone in time to treatment failure as defined as: study discontinuation due to Adverse Events; psychiatric hospitalization; or requiring a change in antidepressant treatment. Time to treatment failure may be ascertained as the treating physician's determination of a study discontinuation due to lack of efficacy; withdrawal due to a treatment related adverse event a psychiatric hospitalization; or the patient requiring any change in their baseline antidepressant, mood stabilizer, or antipsychotic medication. Titration or change in timing of administration of study medication will not be considered a failure of therapy. Lack of efficacy is defined as the need to implement a new treatment plan or an increase in suicidal ideation (a score of 4 or 5 on the C-SSRS, emergent suicidality requiring hospitalization), or increase in depressive symptoms (a score increase of \geq 5 for two consecutive visits on the MADRS total score). The need to implement a new treatment plan includes the addition of new antidepressant medication or somatic treatment (e.g. ECT or rTMS treatment) or an escalation of care such as hospitalization (i.e. moving the patient from outpatient care to initiating inpatient, partial or day hospitalization). Time to failure will be assessed using a Kaplan-Meier lifetable. The formal hypothesis test will be to detect a 0.421 hazard ratio (HR) with 80% power for a two-sided test using a proportional hazard model; a 0.545 hazard ratio reaches two-sided p=0.05.

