7.5 Overview

This is a group sequential, multicenter, randomized, double-blind, parallel-group, two-arm study comparing NRX-101 (n=37) to lurasidone (n=37) in a 1:1 ratio for the treatment of bipolar depression in participants with subacute levels of suicidal ideation, as reflected by the patient answering "yes" to item 3 and 4 on the C-SSRS within 4-weeks of screening, and do not require hospitalization.

Participants will be screened to ensure study eligibility prior to randomization on Day 1. Randomized participants will take either oral NRX-101 or lurasidone and placebo, in accordance with their treatment assignment, for 42 days. Participants will return to the investigational site on Day 70 for a follow-up visit (see Study Schema, Figure 3). During these visits, multiple psychometric scales will be completed, and participants will be assessed for safety, including the risk of increase in depression or suicidal ideation to the point where inpatient care or an alternative treatment is indicated.

Figure 3 Study Schema

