16.4.4 Other Efficacy Endpoints of Interest

The following additional endpoints will be recorded and analyzed by treatment group:

- Dose per treatment group
- Suicide rates (attempted and completed)
- Time to all-cause study discontinuation (and reason for discontinuation) due to any reason such as withdrawal due to an adverse event, or patient or investigator decision to withdraw
- Rate of participants who achieve a resolution of suicide risk by Clinical Global Judgement of Suicide Risk [CGI-SR] 0 or 1) or by MADRS (suicidal ideation item #10 of 0 or 1)
- Proportion of participants who are treated with new SSRIs or have increased SSRI dosages
- Proportion of participants who discontinue SSRIs or have reduced SSRI dosages
- Efficacy for each MADRS factor; mania, depression, irritability, anxiety, and psychosis

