16.6.2 Power and Significance

These sample size calculations are based on the alternative hypothesis corresponding to a 0.66 effect size which corresponds to a mean 8.85-unit MADRS-10 advantage change from baseline for NRX-101 vs control. A total of 74 subjects are to be randomized 1:1 to support the final analysis. As summarized below in Table 6, there is 80% power to detect a 0.66 effect size; a

0.462 effect size would reach two-sided p=0.05. A 0.462 (moderate) effect size reflects a 50 percent drop (based on lurasidone published data) in mean change from baseline for lurasidone with an assumed standard deviation of 13.4; this approximately corresponds to a -16 mean CFB for NRX-101 and a -10 mean CFB for lurasidone.

Table 6 MADRS-10 Change From Baseline Outcomes: T-tests

	Power	Significance
Test significance level, α	0.05	0.05
1 or 2 sided test	2	2
Effect size, $d = m_1 - m_2 / s$	0.66	0.462
Power (%)	80	NA
N per group	37	37

The secondary efficacy hypotheses will also be evaluated using a hierarchical testing strategy where testing continues as long as two-sided p<0.05 is reached. The first such hypothesis to be tested will be for primary endpoint MADRS change from baseline to endpoint, then change from baseline in CGI-SS, followed by time to treatment failure in the NRX-101 and lurasidone groups.

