16.8.3 Conventions

Study visit dates will be analyzed using the nominal visit instead of the actual visit date.

Means, mean changes, standard deviations, and ranges will be presented separately for each treatment group. These endpoints will be evaluated using a paired t-test and between study treatment groups using an unpaired t-test at each time; these p-values will be presented as descriptive statistics.

For continuous variables, the mean, standard deviation, minimum, median and maximum will be presented, together with the total number of observations and the number of missing and non-missing values.

For ordinal and categorical variables, absolute and relative frequencies will be reported. Relative frequencies will be based on all observations and reported as percentages. Unless otherwise specified, percentages will be based on the number of participants with data and will not be calculated for missing categories.

Adverse events, medical histories, and concomitant medications will be reported on a patient and an event basis. Percentages will be calculated using the number of participants in the Safety population analysis set as the denominator.

All hypotheses will be tested at 5 percent (final analysis) level of significance using a two-sided test unless otherwise specified.

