### **19.3 Conventions**

Study visit dates will be analyzed using the nominal visit instead of the actual visit date.

Means, mean changes, standard deviations, and ranges will be presented separately for each treatment group. These endpoints will be evaluated using a paired t-test and between study treatment groups using an unpaired t-test at each time; these p-values will be presented as descriptive statistics.

For continuous variables, the mean, standard deviation, minimum, median and maximum will be presented, together with the total number of observations and the number of missing and non-missing values.

For ordinal and categorical variables, absolute and relative frequencies will be reported. Relative frequencies will be based on all observations and reported as percentages. Unless otherwise specified, percentages will be based on the number of participants with data and will not be calculated for missing categories.

Adverse events, medical histories, and concomitant medications will be reported on a patient and an event basis. Percentages will be calculated using the number of participants in the Safety population analysis set as the denominator.

All hypotheses will be tested at 5 percent (final analysis) level of significance using a two-sided test unless otherwise specified.

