## 20. STATISTICAL METHODOLOGY

### 20.1 General Methodology

The Mixed-Effect Model Repeated Measure (MMRM) will be the primary analysis for the primary efficacy endpoint (MADRS change from baseline); an unpaired t-test will be a secondary analysis. The proportional hazard model (PHREG) will be the primary analysis for time to event endpoints (time to remission, time to discontinuation); the unstratified log rank test will be a secondary analysis. The MMRM and PHREG models will all include treatment and the following four baseline covariates:

- sex
- mood stabilizer use
- anti-psychotic use
- evidence of suicide event in their lifetime.

All primary analyses will be in the mITT population as primary and repeated in the Per Protocol population if >5 percent are excluded.

All of the instruments used to measure SSIB or depression constitute serial continuous and ordinal outcomes that will be analyzed using MMRM with LOCF to account for missing data and early discontinuations. The models will include treatment group, study visit, the interaction between study visit and treatment group, the baseline level of the variable being analyzed, and the above four pre-defined baseline stratification factors as fixed effects. The primary endpoint change from baseline MADRS-10 will be analyzed using the MMRM model which will include baseline MADRS; treatment group; study visit; study visit\*treatment; sex, mood stabilizer use, anti-psychotic use, and evidence of suicide event in their lifetime as defined above. An unstructured error structure will be assumed.

SAS PROC MIXED will be used for continuous endpoints.

In addition, supportive analyses will be performed using multiple imputation which will be performed to address any missing data. The method of Little and Rubin will be used. The presentation of the results for the primary efficacy endpoints using the ITT population will be based on the observed data with multiple imputation for missing endpoint data using SAS PROC MI. Missing data will be imputed using MCMC imputation under the assumption of a missing at random using the mITT population. The SAS® procedure PROC MI will be used for the MCMC imputation of 25 complete data sets.

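### The nominal-visit convention has no exception for time-to-event endpoints and PHREG is named without a tie method, so the time-to-treatment-failure hazard ratio can be pulled towards 1 at a cost of a few points of power

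*Protocol*

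**What the plan says.** Protocol 16.3.3 and SAP 16.3 test TTF with a proportional hazards model. The test is planned "to detect a 0.421 hazard ratio (HR) with 80% power for a two-sided test using a proportional hazard model", and "a 0.545 hazard ratio reaches two-sided p=0.05". TTF comes third in the testing order (Protocol 16.6.2, SAP 18.3): the primary MADRS test, "then change from baseline in CGI-SS, followed by time to treatment failure in the NRX-101 and lurasidone groups". No event count or failure rate is given.

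On analysis, SAP 20.1 says: "The proportional hazard model (PHREG) will be the primary analysis for time to event endpoints". Its examples are time to remission and time to discontinuation, and SAP 20.2 repeats the proportional hazards model as primary for the other time-to-event outcomes. Neither document names a method for tied times.

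On timing, SAP 19.3 (and Protocol 16.8.3 in the same words) says: "Study visit dates will be analyzed using the nominal visit instead of the actual visit date". No endpoint is excepted. The schedule (Table 1 in both documents) has post-baseline treatment visits on Days 7, 14 and 28 and a last visit that serves for both early termination and Day 42. Neither document gives an event-date or censoring rule for TTF.

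**The concern.** TTF is a composite. Psychiatric admission, a medication change and withdrawal for an adverse event happen on calendar dates. The C-SSRS criterion and the MADRS criterion (a sustained rise over two visits) are normally seen only when the scale is administered, so the visit date is their natural event date. The general convention turns that date into a nominal day. All visit-detected failures then share at most four time points, and many participants fail at the same recorded time.

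A proportional hazards fit must then choose a tie method. Breslow's approximation keeps every tied failure in the risk set for all the others. When a large share of the risk set fails at one time, it shrinks the hazard ratio towards 1 and overstates the standard error. Breslow is PHREG's default (a property of the software, not a statement in the documents), so a program written from the SAP with no tie option would use it. At stake are some power in a formally tested endpoint and an attenuated effect estimate. Dates and tie method should not be left to choose after unblinding.

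**Working it through.** **Inputs.** Alternative hazard ratio 0.421, 80% power, and 0.545 as the ratio at p = 0.05 (Protocol 16.3.3). Two-sided 5%: "All hypotheses will be tested at 5 percent (final analysis) level of significance using a two-sided test unless otherwise specified" (Protocol 16.8.3). Sample size: "comparing NRX-101 (n=37) to lurasidone (n=37) in a 1:1 ratio" (Protocol 7.5). Visits on Days 7, 14, 28 and 42 (Table 1). Assumed: exponential failure times, a single treatment covariate, and no dropout unless stated.

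**1. The plan's own figures.** With 1:1 allocation, the ratio that just reaches significance is exp(−1.96 × 2/√d). Setting it to 0.545 gives d = 4 × 1.96² / (ln 0.545)² = 41.7, so 42 failures, or 42/74 = 57% of participants. Power at 0.421 with 42 failures is Φ(√42/2 × 0.865 − 1.96) = Φ(0.84) = 80.0%. Both printed figures reproduce. The formula assumes untied, continuous times.

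**2. Failure rates behind 42 events.** Solving 37 × [p + 1 − (1 − p)^0.421] = 42 gives p = 72.0% on lurasidone and 41.5% on NRX-101 by Day 42.

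**3. Why Breslow shrinks the ratio.** At a single tied time with no other events, the Breslow estimate is the ratio of the two risks. The lurasidone cumulative hazard over 42 days is −ln(1 − 0.720) = 1.273.
- 7-day interval: hazards 0.2122 and 0.421 × 0.2122 = 0.0893; risks 0.191 and 0.0854; ratio 0.447.
- 14-day interval: hazards 0.4243 and 0.1787; risks 0.346 and 0.164; ratio 0.473.

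A fit on the four visits should therefore land between 0.447 and 0.473 rather than at 0.421.

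**4. Simulation.** 37 per arm, true ratio 0.421, 42 expected failures, Wald test. Visit-dated failures move to the next scheduled visit; the rest keep their actual day. Ranges are over repeated runs (Monte Carlo error about 0.7 to 0.9 points).

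| Dating of failures | Power, Breslow | Fitted HR, Breslow | Power, Efron |
|---|---|---|---|
| Actual days | 78–79.5% | 0.42 | same |
| 25–50% on nominal visits | 75–78% | 0.43 | 78–79% |
| All on nominal visits | 70–73% | 0.46 | 78–80% |

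The fitted 0.46 agrees with step 3. The log-rank test, planned as secondary, gives 78.9% on nominal visits and 78.9% on actual days.

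**5. Sensitivity, all failures on nominal visits.** With an assumed 20% dropout: actual days 74.2%, Breslow 66.4%, Efron 73.3%. With 20 failures instead of 42 and no dropout: 41.2%, 37.8% and 41.4%. Fewer failures mean fewer ties and a smaller tie loss, although total power is far lower.

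**6. Type I error.** At a true ratio of 1 with all failures on nominal visits, Breslow rejects in about 2 to 3% of trials and Efron in about 5%. The distortion is conservative.

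**The case against.** The strongest reply is that the convention speaks of visit dates, not event dates, and the text after it in SAP 19.3 concerns by-visit means and t-tests. Most TTF components are not visits. Adverse event, hospitalisation and medication dates are all collected (Protocol 15.2.1, 15.2.4 and 15.3.1), and SAP 20.2 has failure judged in real time. Unscheduled visits are allowed (Protocol 9.1) and have no nominal day. A sensible programmer would use the real dates and might well choose Efron. All of this stands, and it makes the loss conditional. It does not close the gap, because the scale-based components depend on visits and no rule says how to date them.

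It is also fair that grouping alone costs almost nothing, since the loss needs Breslow as well. The bias favours no effect, and TTF is tested formally only after MADRS and CGI-SS have both succeeded. These points limit the importance; they do not argue against the remedy.

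Two stronger readings are tempting. One is that every early exit is timed at Day 42 because early termination shares that visit. Simulated Breslow power would then be about 58 to 60% with half of failures filed there and about 34% with all of them, and the curve for "Time to all-cause study discontinuation" would be flat until Day 42. No section says this. The shared column shows that the same assessments are done on either occasion, and such timing would empty the discontinuation endpoint of meaning. These figures are a worst case only. The other reading is that the test does not deliver its 80%. The 80% reproduces at 42 failures, and a shortfall from ties arises only if visit dating and Breslow ties are both used.

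**Conclusion.** The point holds as a gap in specification. The plan leaves open how visit-detected failures are timed and how ties are handled, and the most literal implementation costs TTF some power and attenuates its hazard ratio. If a quarter to a half of failures are visit-dated, the loss is about 1 to 4 points from about 79%. If all are, it is about 7 to 8 points, with a fitted ratio of about 0.46 against a true 0.421. Efron ties remove most or all of this.

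These sizes rest on about 42 failures, exponential times, no covariates and Breslow ties. The 42 is implied by the plan's figures and stated nowhere; the visit-dated share is unknown, hence the range. The direction is conservative, so a positive TTF result would not be in doubt. This is a worthwhile improvement at no cost, not a threat to the trial's main conclusion.

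**What to change.** - **SAP 19.3:** limit the nominal-visit rule to by-visit summaries and the MMRM.
- **TTF, time to discontinuation and time to remission:** measure time in actual days from randomisation. Use the event's own date (admission, medication change, withdrawal) or, for scale-based events, the actual visit date. State the censoring date, and state that early terminations are not timed at Day 42.
- **SAP 20.1 and 20.2:** specify PHREG with TIES=EFRON or TIES=EXACT.

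The cost is a few lines of SAP wording and one program option, to be settled before unblinding. The event, medication and hospitalisation dates are already collected, and no visit, sample size or testing order changes.

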16.4 Efficacy Endpoints

16.4.1 Primary Efficacy Endpoints

The primary efficacy endpoint is the change from baseline in the total MADRS score as measured by psychometric raters assessed over 42 days post randomization by mixed-model repeated measures analysis.

16.4.2 Secondary Efficacy Endpoints

The key secondary efficacy endpoints are:

- Change from baseline in CGI-SS score as measured by treating prescriber assessed over 42 days post randomization by mixed-model repeated measures analysis.
- Time to Treatment Failure (TTF) A Kaplan-Meier lifetable will be constructed for the time to failure of therapy. Failure of therapy will be defined as the treating physician's determination of a study discontinuation due to lack of efficacy; withdrawal due to a treatment related adverse event a psychiatric hospitalization; or the patient requiring any change in their baseline antidepressant, mood stabilizer, or antipsychotic medication. Titration or change in timing of administration of study medication will not be considered a failure of therapy.

The additional efficacy endpoints are:

- Change from baseline to endpoint in Suicidal Thoughts on the MADRS (MADRS item 10)
- Mean change from baseline to Day 14 in total MADRS score
- Change from baseline to endpoint in each item of the Suicide Ideation and Behavior Assessment Tool (SIBAT) Module 7 (clinical global impressions of frequency of suicidal thinking, severity of suicidality, and imminent and long-term risks)

16.4.3 Other Exploratory Efficacy Endpoints

The following other efficacy endpoints will be explored:

• Remission from suicidality: A Kaplan-Meier lifetable will be constructed for the remission duration from response onset where remission is defined as reaching CSSR-S ≤ 2 and remaining through the study. Remission rate is defined as percent remaining in remission.

Collectively, symptom improvement will be evaluated by assessing changes in the secondary outcome measures within and between treatment groups for each of the following at the times specified on the Schedule of Study Activities:

- Montgomery Asberg Depression Rating Scale (MADRS) (Montgomery, Åsberg 1979)
- Clinical Global Impression of Severity of Suicidality Scale (CGI-SS)

- Concise Health Risk Tracking Self Report (CHRT-SR) and Clinician Rating (CHRT-C) scales (Trivedi et al., 2011)
- Brief Psychiatric Rating Scale (BPRS) (Overall and Gorham, 1962).

16.4.4 Other Efficacy Endpoints of Interest

The following additional endpoints will be recorded and analyzed by treatment group:

- Dose per treatment group
- Suicide rates (attempted and completed)
- Time to all-cause study discontinuation (and reason for discontinuation) due to any reason such as withdrawal due to an adverse event, or patient or investigator decision to withdraw
- Rate of participants who achieve a resolution of suicide risk by Clinical Global Judgement of Suicide Risk [CGI-SR] 0 or 1) or by MADRS (suicidal ideation item #10 of 0 or 1)
- Proportion of participants who are treated with new SSRIs or have increased SSRI dosages
- Proportion of participants who discontinue SSRIs or have reduced SSRI dosages
- Efficacy for each MADRS factor; mania, depression, irritability, anxiety, and psychosis

16.4.5 Diagnostic Metric

The following metrics will be evaluated at baseline:

• MINI 7.0.2

16.5 Safety Assessments

- Change from baseline to endpoint (Day 42) in C-SSRS score
- Change from baseline to endpoint (Day 14) in C-SSRS score
- Mean change in BARS through Day 42 to assess akathisia
- Percent in remission at Day 42/exit, defined as having achieved a MADRS score of ≤ 10 during the last two visits (14 days)
- Rates of discontinuation between the arms

16.5.1 Overall Adverse Events

Separate and combined safety analyses will be performed for the Safety population. All safety results will be presented separately for each treatment group. Safety endpoints will include adverse events (AEs), vital signs, ECGs, and laboratory parameters.

The principle of treatment emergence will be employed for the analysis of AE data. Treatment emergence is defined as any event that occurred following the initiation of therapy and was not

present at baseline, or one which represents an exacerbation of a condition present prior to study entry (pre-existing).

Unresolved AE outcomes at the end of the study will be followed for an additional seven days or until resolution, whichever occurs earlier.

Adverse events will be classified by the Medical Dictionary for Regulatory Activities (MedDRA). For each study treatment, safety data will be collected and analyzed until treatment-emergent AEs are resolved. The type, incidence, timing (onset, duration), relationship, and severity of treatment-emergent AEs will be reported. Reasons for withdrawal due to AEs will also be reported.

Two-sided Fisher Exact tests will be performed to compare the two treatment groups with respect to incidence at the system order class level and for any preferred terms with >10 percent overall incidence.

